8.1.1 Adverse Events Definitions

8.1.1.1 Adverse Events (21 CFR 312.32(a))

An AE is defined as any untoward medical occurrence associated with the use of a drug in humans, whether or not considered drug related. An AE (also referred to as an adverse experience) can be any unfavorable and unintended sign (e.g., an abnormal laboratory finding), symptom, or disease temporally associated with the use of a drug and does not imply any judgment about causality. An AE can arise with any use of the drug (e.g., off-label use, use in

Confidential and Proprietary

combination with another drug) and with any route of administration, formulation, or dose, including an overdose.

8.1.1.2 Suspected Adverse Reaction (21 CFR 312.32(a))

Suspected adverse reaction means any AE for which there is a reasonable possibility that the drug caused the AE. For the purposes of IND safety reporting, "reasonable possibility" means there is evidence to suggest a causal relationship between the drug and the AE. A suspected adverse reaction implies a lesser degree of certainty about causality than adverse reaction, which means any AE caused by a drug.

8.1.1.3 Unexpected (21 CFR 312.32(a))

An AE or suspected adverse reaction is considered "unexpected" if it is not listed in the Investigator's Brochure or is not listed at the specificity or severity that has been observed; or, if an Investigator's Brochure is not required or available, is not consistent with the risk information described in the general investigational plan or elsewhere in the current application, as amended. For example, under this definition, hepatic necrosis would be unexpected (by virtue of greater severity) if the Investigator's Brochure referred only to elevated hepatic enzymes or hepatitis. Similarly, cerebral thromboembolism and cerebral vasculitis would be unexpected (by virtue of greater specificity) if the Investigator's Brochure listed only cerebral vascular accidents. "Unexpected," as used in this definition, also refers to AEs or suspected adverse reactions that are mentioned in the Investigator's Brochure as occurring with a class of drugs or as anticipated from the pharmacological properties of the drug but are not specifically mentioned as occurring with the particular drug under investigation.

8.1.1.4 Serious Adverse Event (21 CFR 312.32(a))

An AE or suspected adverse reaction is considered "serious" if, in the view of either the Investigator or Sponsor, it results in any of the following outcomes:

- Death
- Life-threatening AE
- Inpatient hospitalization or prolongation of existing hospitalization
- Persistent or significant incapacity or substantial disruption of the ability to conduct normal life functions
- Congenital anomaly/birth defect.

Important medical events that may not result in death, be life-threatening, or require hospitalization may be considered serious when, based upon appropriate medical judgment, they may jeopardize the patient or may require medical or surgical intervention to prevent one of the outcomes listed in this definition. Examples of such medical events include allergic bronchospasm requiring intensive treatment in an emergency room or at home, blood dyscrasias or convulsions that do not result in inpatient hospitalization, or the development of drug dependency or drug abuse.

Amendment 3: 24 October 2020 Confidential and Proprietary

Rain Therapeutics Inc.

8.1.1.5 **Serious Unexpected Suspected Adverse Reaction**

A suspected adverse reaction that is both serious and unexpected will be reported in an expedited manner.

Rain Therapeutics (or designee) will report all serious unexpected suspected adverse reactions (serious, related, and unexpected AEs) to the regulatory agencies in the countries where this study is conducted per local country requirements.

- Regulatory agencies will be notified (e.g., by telephone, facsimile transmission, or in writing) of all fatal and/or life-threatening suspected adverse drug reactions as soon as possible but no later than 7 calendar days after first knowledge by the Sponsor that a case qualifies, followed by as complete a report as possible within 8 additional calendar days.
- Serious, unexpected suspected adverse reactions that are not fatal or life-threatening must be filed as soon as possible but no later than 15 calendar days after first knowledge by the Sponsor that the case meets the minimum criteria for expedited reporting.

8.2 **Adverse Events Reporting**

8.2.1 **Adverse Event Term**

AEs must be reported using standard medical terminology. The use of abbreviations (standard and nonstandard) should be avoided to help ensure a clear understanding of the event. An example of a standard abbreviation that may have several meanings is "MI" which could mean "myocardial infarction" or "mitral insufficiency." All AE terms will be coded using a standardized dictionary (i.e., Medical Dictionary for Regulatory Activities [MedDRA®]). Generally, when reporting a well-known and understood condition, it is preferable to report the overall diagnosis rather that the individual signs and symptoms; the exception to this rule in this study is when the patient experiences an infusion reaction (i.e., infusion-related reaction). The term "intermittent" should be avoided as the duration and incidence of events helps in understanding the safety profile of the study drug.

8.2.2 **Adverse Event Severity**

AEs will be reported at the highest experienced. AE severity will be graded according to NCI CTCAE v5.0. A copy of the document will be provided to investigational sites and an electronic version is available at:

https://ctep.cancer.gov/protocolDevelopment/electronic applications/docs/CTCAE v5 Quick R eference 8.5x11.pdf

Events not listed in NCI CTCAE will be graded according to the criteria described in Table 10.

Confidential and Proprietary

Table 10: Severity Grading Guideline for Adverse Events Not Listed in NCI CTCAE

Adverse Events Not Listed in NCI CTCAE v5.0			
Grade	Description		
1	Mild; Asymptomatic or mild symptoms; Clinical or diagnostic observations only; Intervention not indicated		
2	Moderate; Minimal, local or noninvasive intervention indicated; Limiting age-appropriate instrumental activities of daily living*		
3	Severe or medically significant but not immediately life-threatening; Hospitalization or prolongation of hospitalization indicated; Disabling; Limiting self-care activities of daily living**		
4	Life-threatening consequences; Urgent intervention indicated		
5	Death related to adverse event		

Adapted from NCI CTCAE v5.0

NCI CTCAE = National Cancer Institute Common Terminology Criteria for Adverse Events

Note: A semicolon indicates "or" within the description of the grade.

8.2.3 Adverse Event Duration

The start date (the date that the event was first noticed) and the end date (the date that the event had completely resolved or returned to baseline) will be recorded. If the exact date is not known, the best estimate should be reported.

All AEs will be followed until stabilization or resolution.

8.2.4 Adverse Event Causality

Where the determination of the relationship of the AE to study drug rests on medical judgment, the determination must be made with the appropriate involvement of the Investigator, or, if the Investigator is not a physician, a designated sub-investigator who is a physician.

Using the following criteria, Investigators will assess whether there is a reasonable possibility that the study drug caused or contributed to the AE.

Related

• The time sequence between the onset of the AE and study drug administration is consistent with the event being related to study drug; and/or

^{*}Instrumental activities of daily living refer to preparing meals, shopping for groceries or clothes, using the telephone, managing money, etc.

^{**}Self-care activities of daily living refer to bathing, dressing, and undressing, feeding self, using the toilet, taking medications, and not bedridden.

Confidential and Proprietary

• There is a possible biologic mechanism for study drug causing or contributing to the AE; and the AE may or may not be attributed to concurrent/underlying illness, other drugs, or procedures.

Not Related

- Another cause of the AE is most likely; and/or
- The time sequence between the onset of the AE and study drug administration is inconsistent with a causal relationship; and/or
- A causal relationship is considered biologically unlikely.

8.3 Serious Adverse Events Reporting

Suspected adverse reactions that meet the definition of serious (see Section 8.1.1.5) require accelerated reporting.

To enable Rain Therapeutics to meet the expedited reporting requirements, Investigators must report all SAEs regardless of causality immediately (within 24 hours of learning of the event). SAEs will be reported by submitting a Serious Adverse Events Report to:

[contact]

An event that results in hospitalization or prolongs an existing hospitalization will not be considered an SAE, if the only reason for that hospitalization or prolongation is:

- Administration of study treatment
- Administration of study procedures
- Placement of permanent intravenous catheter
- Hospice placement due to PD

8.4 Reporting Infusion-related Reactions

Infusion-related reactions (IRRs) are defined as "a disorder characterized by adverse reaction to the infusion of pharmacological or biological substances." The incidence and severity or IRRs will be collected in the eCRF designed to collected tarloxotinib infusion details; individual signs and symptoms of IRRs will be reported as AEs. Investigators will indicate which reported AEs were part of an IRR.

Confidential and Proprietary

Table 11: Severity Grading Guideline for Infusion-Related Reactions

Infusion-Related Reactions		
Grade	Description	
1	Mild transient reaction; infusion interruption not indicated; intervention not indicated	
2	Therapy or infusion interruption indicated but responds promptly to symptomatic treatment (e.g., antihistamines, nonsteroidal anti-inflammatory drugs, narcotics, intravenous fluids); prophylactic medications indicated for ≤ 24 hours	
3	Prolonged (e.g., not rapidly responsive to symptomatic medication and/or brief interruption of infusion); recurrence of symptoms following initial improvement; hospitalization indicated for clinical sequelae	
4	Life-threatening consequences; Urgent intervention indicated	
5	Death	

Adapted from National Cancer Institute Common Terminology Criteria for Adverse Events v5.0

Note: A semicolon indicates "or" within the description of the grade.

8.5 Reporting QTc Prolongation

QT prolongation is not unexpected but it is an AE of special interest (AESI). Grade 3 AESIs require expedited reporting to the Sponsor. ECGs will be obtained throughout the study and will be read locally at the investigational sites. Grade 3 QTc prolongation (absolute QTcF of \geq 501 msec or QTcF increase of > 60 msec relative to pre-infusion) or Grade 4 QTc prolongation will be reported as an AESI.

Any apparent Grade 3 AESIs should be verified by manually measuring at least 3 complexes within the ECG and determining the average QTcF.

AESIs will be reported by submitting an AESI Report to:

[contact]

All events of Grade 3 QTc prolongation (absolute QTcF of \geq 501 msec or QTcF increase of \geq 60 msec relative to pre-infusion) or Grade 4 QTc prolongation will be reported as an AESI unless the event met the criteria of serious (see Section 8.1.1.4) in which case it will be reported as an SAE.

Confidential and Proprietary

Table 12: NCI CTCAE Grading of ECG QTc Prolongation (Medical Dictionary of Regulatory Activities Code: 10014383)

ECG QTc Prolongation NCI CTCAE Grade					
1	2	3	4	5	
Average QTc	Average QTc	Average	Torsade de Pointes	Not applicable	
450 to 480 msec	481 to 500 msec	$QTc \ge 501 \text{ msec}$	OR		
		OR	polymorphic		
		> 60 msec change	ventricular		
		from baseline*	tachycardia		
			OR		
			signs/symptoms of		
			serious arrhythmia		

Adapted from NCI CTCAE v5.0

ECG = electrocardiogram; NCI CTCAE = National Cancer Institute Common Terminology Criteria for Adverse Events; QTc = corrected QT interval; QTcF = corrected QTc interval as calculated according to Fridericia's formula

Definition of QTc prolongation: A finding of a cardiac dysrhythmia characterized by an abnormally long QTc * Although a Grade 3 event (≥ 501 msec OR > 60 msec change from baseline) is reportable as an adverse event of special interest, dose reductions are not required for patients with absolute QTcF ≤ 500 msec and a ≤ 60 msec QTcF change from baseline.

8.6 Reporting Disease Progression and Death

PD, also referred to a disease progression, and death due to disease progression are study endpoints and information related to these events will collected in eCRFs specifically designed to collect these data. These events will not be reported as AE/SAEs unless the Investigator feels that these are accelerated, atypical, or related to study treatment. Deaths occurring within the 30 days after the last study treatment will be recorded. Any death that the Investigator feels is related to study treatment must be reported to the Sponsor as an SAE within 1 business day of first becoming aware of the death. Deaths occurring more than 30 days after study completion that are not considered related to study treatment may be reported cumulatively on a quarterly basis. Reports of all deaths must be communicated as soon as possible to the appropriate IRB/IEC and/or reported in accordance with local laws and regulations.

If an autopsy is performed, a copy of the report will be requested and provided to the Sponsor, if available.

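### Protocol Sections 8.3 and 8.6 set two different deadlines, 24 hours and 1 business day, for a site to report the same treatment-related death to the Sponsor

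*Protocol*

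**What the plan says.** Four parts of the protocol bear on this point.

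- **Section 8.3 (SAE reporting).** Investigators must "report all SAEs regardless of causality immediately (within 24 hours of learning of the event". The stated purpose is "To enable Rain Therapeutics to meet the expedited reporting requirements". There is no separate rule for fatal events.
- **Section 8.1.1.4 (definition of serious).** An event is serious if, "in the view of either the Investigator or Sponsor, it results in any of the following outcomes". Death heads the list that follows.
- **Section 8.6 (progression and death).** A death that the Investigator considers treatment-related "must be reported to the Sponsor as an SAE within 1 business day of first becoming aware of the death". The same section keeps progression, and death due to progression, out of AE/SAE reporting with an exception: "These events will not be reported as AE/SAEs unless the Investigator feels that these are accelerated, atypical, or related to study treatment". It also gives a slower route to one group: "Deaths occurring more than 30 days after study completion that are not considered related to study treatment may be reported cumulatively on a quarterly basis".
- **Section 8.1.1.5 (Sponsor to regulators).** Fatal or life-threatening suspected reactions go to the regulatory agencies "no later than 7 calendar days after first knowledge by the Sponsor that a case qualifies".

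The SAP sets no timeline for reports from the site to the Sponsor.

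**The concern.** A treatment-related death meets the definition of an SAE, and Section 8.6 itself says it is reported as one. It therefore falls under both limits. Section 8.6 is the section whose title names death, so a site dealing with one is likely to look there. A site that follows it literally over a weekend can meet Section 8.6 and miss Section 8.3. A non-fatal related SAE has only the 24-hour limit. The documents give no reason for offering a fatal one a longer alternative.

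What is at stake is how soon the Sponsor knows. Section 11.4 makes early termination for a hazard depend on the Investigator, the Sponsor or the Medical Monitor becoming aware of it. The protocol describes no independent monitoring committee and no pause rule based on event counts. Section 2.6 states that QT prolongation can, rarely, lead to fatal rhythms. Prompt site reporting is therefore an important source of information for the Sponsor.

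**Working it through.** The plan gives no figure to reproduce. The check compares the texts and then converts 1 business day into hours.

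**Step 1. Do both limits apply to the same event?**

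| Question | Section 8.3 | Section 8.6 |
|---|---|---|
| Event covered | Every SAE, whatever the causality | Death considered treatment-related, reported as an SAE |
| Clock starts | When the site learns of the event | When the site becomes aware of the death |
| Limit | Immediately, at most 24 hours | 1 business day; no requirement of immediacy |
| Cross-reference to the other section | None | None |

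The exclusions do not separate the two. Section 8.3 lists hospitalizations that do not count as SAEs, and none concerns death. The progression rule in Section 8.6 makes an exception for related events. The quarterly route is for late, unrelated deaths. A related death is therefore subject to both limits.

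**Step 2. How long is 1 business day?** The term is undefined. It also appears in Section 6.1, for the Medical Monitor's eligibility response, again without a definition. Assume working days are Monday to Friday and take two readings:

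- (a) the same clock time on the next working day;
- (b) 17:00 on the next working day.

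For awareness between 09:00 and 20:00:

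| Site becomes aware | Reading (a) | Reading (b) | Section 8.3 |
|---|---|---|---|
| Sunday to Thursday, no holiday | 24 h | 21 to 32 h | 24 h |
| Saturday | 48 h | 45 to 56 h | 24 h |
| Friday | 72 h | 69 to 80 h | 24 h |
| Friday before a Monday holiday | 96 h | 93 to 104 h | 24 h |

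**Step 3. Reference case.** At 17:00 on Friday the two readings agree.

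- Section 8.3: Friday 17:00 + 24 h = Saturday 17:00.
- Section 8.6: Monday 17:00 = 3 × 24 = 72 h. With a Monday holiday, Tuesday 17:00 = 4 × 24 = 96 h.
- Difference: 72 − 24 = 48 h; 96 − 24 = 72 h.

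**Step 4. Effect on the regulatory clock.** The 7 calendar days run from the Sponsor's knowledge, so site time comes in front of them. For a death that qualifies, and if the Sponsor recognises this on receipt, the longest interval from site awareness to regulator is 1 + 7 = 8 days under Section 8.3. Under Section 8.6 in the reference case it is 3 + 7 = 10 days, or 4 + 7 = 11 days with the holiday. This is the same 48 to 72 hours seen further down the line, not an additional delay.

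**The case against.** The strongest reply is that the stricter rule already applies. Section 8.3 covers all SAEs without a carve-out, and Section 8.6 calls the death an SAE, so a site that uses only the longer limit breaches Section 8.3. This stands, and it means Section 8.6 cannot be read as exempting related deaths from the 24-hour rule. It does not remove the conflict, because nothing tells the site which section governs.

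Three other limits on the point also stand.

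- Outside weekends and holidays the limits nearly coincide. Under reading (b), a report late on a midweek evening would be due slightly sooner under Section 8.6.
- A life-threatening event or a hospitalization before the death is itself an SAE with its own 24-hour limit. The full gap arises only when the death is the site's first knowledge.
- According to SAP Section 4 the trial was discontinued, with 41 subjects enrolled and the database locked on 23 April 2021. The practical value now lies in later protocols that reuse this text.

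A reader might also infer three stronger things that the documents do not support.

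- *That related deaths have the slowest route of all.* Late unrelated deaths may be reported quarterly, and Section 8.5 gives no hour limit for adverse events of special interest. The comparison holds only among treatment-related SAEs.
- *That nobody outside the site would know over the weekend.* Section 8.6 also requires all deaths to be communicated to the IRB/IEC as soon as possible. That notice does not go to the Sponsor, but it does leave the site.
- *That a calculable share of patients would receive an avoidable infusion.* This needs a single report to halt dosing at every site at once. Section 11.4 says only that the study may be terminated after consultation.

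**Conclusion.** The point holds as an internal contradiction. Sections 8.3 and 8.6 give different limits for reporting a treatment-related death to the Sponsor, and the protocol does not say which prevails. In the Friday 17:00 case the longer limit allows 72 to 96 hours against 24, a difference of 48 to 72 hours, ahead of the Sponsor's regulatory clock. The size rests on a Monday-to-Friday working week, on a business day ending at the same time or at 17:00 on the next working day, and on the death being the site's first knowledge of the event. The contradiction itself rests on none of these. No sample size, error rate, endpoint or analysis is affected. It is a limited defect in safety reporting that should be corrected.

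**What to change.** In Section 8.6, replace the business-day limit for treatment-related deaths with the limit already in Section 8.3: immediately, and no later than 24 hours after the site learns of the event. Add a cross-reference to Section 8.3 so that one section governs. Make the same change in the site safety-reporting instructions. The quarterly route for late unrelated deaths can stay as it is.

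The cost is one phrase and one cross-reference. Sites already operate the 24-hour route for other SAEs, so no new process is needed.

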8.7 Electrocardiogram Monitoring

Standard 12-lead ECGs will be performed locally using a calibrated digital ECG machine capable of providing automated measurements. All ECG tracings will be acquired with the patient in the supine position after the patient has been resting for at least approximately 5 minutes. ECG tracings will be measured and interpreted locally by a cardiologist or other qualified health care professional in accordance with institutional standard of care.

Immediate medical management of patients will be based on the automated reading obtained at the investigational site (all clinically significant ECG readings should be manually verified by a qualified individual). If the Investigator has any question regarding the local automated read, a local cardiologist should be consulted.

Confidential and Proprietary

For patients with QT prolongation during tarloxotinib infusion, ECGs may need to be conducted more frequently than indicated in the Schedule of Events, depending on the degree of prolongation (see Section 6.9.2.1).

Rain will review all reported ECG measurements at least quarterly.

8.8 Vital Sign Assessments

The following vital signs will be assessed after the patient has been sitting for approximately 5 minutes. Vital signs will be obtained at each visit and prior to and following the start of each tarloxotinib infusion. Vital signs to be measured include:

- Blood pressure (systolic and diastolic; mmHg)
- Heart rate (beats per minute)
- Body temperature (°C)
- Respiration rate (breaths per minute)

8.9 Clinical Laboratory Assessments

Clinical laboratory assessments will be performed by each institution's local laboratory. The following laboratory variables (Table 13) will be collected in accordance with the Schedule of Events. All clinically significant unscheduled laboratory results will be recorded and all clinically significant laboratory results (scheduled and unscheduled) obtained during the study period will be reported as AEs (e.g., \geq Grade 2 AST, ALT, or serum bilirubin).

Confidential and Proprietary

Table 13: Clinical Laboratory Assessments

Serum Chemistry:	Sodium	Creatinine	
	Potassium	Bilirubin	
	Chloride	Aspartate aminotransferase increased	
	Bicarbonate	Alanine aminotransferase increased	
	Calcium	Alkaline phosphatase	
	Magnesium	Albumin	
	Phosphorous	Total protein	
	Glucose		
	Blood urea nitrogen		
Hematology:	Hematocrit		
	Hemoglobin		
	White blood cell count with differential (reported as absolute counts)		
	Total neutrophils		
	• Lymphocytes		
	Monocytes		
	• Eosinophils		
	Basophils		
	Platelet count		
Urinalysis:	Protein		
	Glucose		
	Ketones		
	Urobilinogen		
	Occult blood		
	Microscopic sediment evaluation, as clinically indicated		
Pregnancy Test:	In women with childbearing potential only: serum β -human chorionic gonadotropin pregnancy test, urine, or urine dipstick		

